#### **6.4. Change from Protocol Specified Efficacy Analyses**

The protocol states that the proportion of participants progressing to requiring oxygen supplementation by Day 28 will be estimated using the Kaplan-Meier method and compared between the 2 treatment groups using a log-rank test. In the SAP, the number and percentage of participants progressing to requiring oxygen supplementation by Day 28 will be summarized and compared between treatment groups using the Fisher Exact test due to very small number of participants progressing to requiring oxygen supplementation.

## 7. SAFETY ANALYSES

### 7.1. Adverse Events and Deaths

Safety data will be summarized for the participants in the safety analysis set. All safety data collected on or after the date that study drug was first dispensed through 30 days after last dose will be summarized by treatment group for the Safety Analysis Set, unless specified otherwise. All safety data will be included in data listings.

#### 7.1.1. Adverse Event Dictionary

Clinical and laboratory adverse events (AEs) will be coded using the current version of MedDRA. System organ class (SOC), high-level group term (HLGT), high-level term (HLT), preferred term (PT), and lower-level term (LLT) will be provided in the AE dataset.

#### 7.1.2. Adverse Event Severity

The severity of AEs will be graded using the Division of AIDS (DAIDS) Table for Grading the Severity of Adult and Pediatric Adverse Events, Version 2.1 dated July 2017. For each episode, the highest grade attained should be reported as defined in the grading scale. The DAIDS scale is available at the following location:

<https://rsc.niaid.nih.gov/sites/default/files/daidsgradingcorrectedv21.pdf>

Adverse events are graded by the investigator as Grade 1 (mild), Grade 2 (moderate), Grade 3 (severe), Grade 4 (life threatening) or Grade 5 (fatal) according to toxicity criteria specified in the document above. The severity grade of events for which the investigator did not record severity will be left as “missing” for data listings.

#### 7.1.3. Relationship of Adverse Events to Study Drug

Related AEs are those for which the investigator selected “Related” on the AE CRF to the question of “Related to Study Treatment.” Relatedness will always default to the investigator’s choice, not that of the medical monitor. Events for which the investigator did not record relationship to study drug will be considered related to study drug for summary purposes. However, by-subject data listings will show the relationship as missing.

#### 7.1.4. Relationship of Adverse Events to Study Procedure

Study procedure-related AEs are those for which the investigator selected “Yes” on the AE CRF to the question of “Related to Study Procedures.” Events for which the investigator did not record relationship to study procedure will be considered as missing. No summary table for relationship of AE to study procedure will be presented.

### **7.1.5.      Serious Adverse Events**

Serious adverse events (SAEs) will be identified and captured as SAEs if the AEs met the definitions of SAEs that were specified in the study protocol. SAEs captured and stored in the clinical database will be reconciled with the SAE database from the Gilead Global Patient Safety (GLPS) Department before data finalization.

### **7.1.6.      Treatment-Emergent Adverse Events**

Proportion of participants with treatment-emergent AEs (TEAEs) is the primary safety endpoint of the study. No statistical comparison will be provided for proportion of participants with TEAE.

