**Statistical Methods:**

The total sample size of the study will be approximately 1264 participants.

A sample size of approximately 1264 participants (632 in each group with 1:1 randomization) achieves > 90% power to detect a ratio of 0.55 (RDV to placebo in proportion of COVID-19 related hospitalization or all-cause death rate, which is equal to a hazard ratio of 0.534) using a 2-sided significance level of 0.05 assuming the overall hospitalization or death rate is 9.3% (12% in the placebo group and 6.6% in the RDV group) and a 5% drop out rate. The sample size provides approximately 80% power to detect a ratio of 0.60 (RDV to placebo). This analysis will be stratified by residence in skilled nursing facility, age (<60 vs ≥60 years), and region (US vs ex-US). An unblinded sample size re-estimation is planned after 50% participants completed Day 28.

The primary endpoint will be analyzed using Cox model with stratification factors as covariates. The null hypothesis being tested is whether the ratio of hospitalization or death is the same for either RDV or placebo treatment. The ratio and 95% confidence interval will be provided.

Treatment-emergent AEs and laboratory abnormalities will be summarized using descriptive statistics and listed by participant.

---

This study will be conducted in accordance with the guidelines of Good Clinical Practice including archiving of essential documents.

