## 2. OBJECTIVES

The purpose of this trial is to evaluate treatment with IV administered RDV in an outpatient setting in participants with confirmed COVID-19 who are at higher risk for disease progression.

The primary objectives of this study are as follows:

- To evaluate the efficacy of RDV in reducing the rate of COVID-19 related hospitalization or all-cause death in non-hospitalized participants with early stage COVID-19
- To evaluate the safety of RDV administered in an outpatient setting

The secondary objectives of this study are as follows:

- To evaluate the efficacy of RDV in reducing the rate of COVID-19 related medically attended visits (MAVs; medical visits attended in person by the participant and a health care professional) or all- cause death in non-hospitalized participants with early stage COVID-19
- To determine the antiviral activity of RDV on SARS-CoV-2 viral load
- To assess the impact of RDV on symptom duration and severity

CCI

A large rectangular area of the page is completely blacked out, indicating redacted content. The text 'CCI' is printed in red at the top left corner of this redacted area.

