#### 8.1.2. Primary Endpoint

The primary endpoints of this study are as follows:

- Composite endpoint of COVID-19 related hospitalization (defined as at least 24 hours of acute care) or all-cause death by Day 28
- Proportion of participants with treatment-emergent AEs

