### **8.6.2. Adverse Events**

Clinical and laboratory AEs will be coded using the Medical Dictionary for Regulatory Activities. System Organ Class, High-Level Group Term, High-Level Term, Preferred Term, and Lower-Level Term will be attached to the clinical database.

Events will be summarized on the basis of the date of onset for the event. A treatment-emergent AE will be defined as any AE that begins on or after the randomization date up to the date of last dose of study drug plus 30 days.

Summaries (number and percentage of participants) of treatment-emergent AEs (by system organ class and preferred term) will be provided by treatment group.

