### 7.1.7. Summaries of Adverse Events and Deaths

Treatment-emergent AEs will be summarized based on the Safety Analysis Set.

The number and percentage of participants who experienced at least 1 TEAE will be provided and summarized by SOC, High lever term (HLT), PT, and treatment group. For other AEs described below, summaries will be provided by system organ class, PT, and treatment group:

- Grade 3 or higher treatment-emergent AEs
- All treatment-emergent study drug-related AEs
- Grade 3 or higher treatment-emergent study drug-related AEs
- All treatment-emergent SAEs
- All treatment-emergent study drug-related SAEs
- All treatment-emergent AEs that caused premature discontinuation from study drug

TEAE and study drug related TEAE will summarized by system organ class, PT, Severity and treatment group.

A brief, high-level summary of the number and percentage of participants who experienced at least 1 TEAE in the categories described above, and treatment emergent deaths will be provided by treatment group. Treatment-emergent death refers to deaths that occurred between the first dose date and the last dose date plus 30 days (inclusive).

Multiple events will be counted only once per participant in each summary. Adverse events will be summarized and listed first in alphabetic order of SOC and HLT within each SOC (if applicable), and then by PT in descending order of total frequency within each SOC. For summaries by severity grade, the most severe grade will be used for those AEs that occurred more than once in an individual participant during the study.

In addition to the above summary tables, all treatment-emergent AEs, treatment-emergent AEs with Grade 3 or higher, treatment-emergent study drug-related AEs, and treatment-emergent study drug-related AEs with Grade 3 or higher, will be summarized by PT only, in descending order of total frequency.

In addition, data listings will be provided for the following:

- All AEs
- Study-Drug-Related AEs
- AEs with severity of Grade 3 or higher
- SAEs

- Study-Drug-Related SAEs
- Deaths
- AEs leading to premature discontinuation of study drug

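### The primary safety endpoint, any TEAE, is reported only as n (%) per arm, with no planned between-arm difference or confidence interval

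*SAP*

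**What the plan says.** Protocol Section 2 sets a primary safety objective: "To evaluate the safety of RDV administered in an outpatient setting". It carries no hypothesis, margin or comparator wording. Protocol 8.1.2 lists "Proportion of participants with treatment-emergent AEs" as one of the two primary endpoints.

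On analysis, the protocol synopsis says: "Treatment-emergent AEs and laboratory abnormalities will be summarized using descriptive statistics and listed by participant". Protocol 8.6.2 adds: "Summaries (number and percentage of participants) of treatment-emergent AEs (by system organ class and preferred term) will be provided by treatment group".

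SAP 7.1.6 confirms the status of the endpoint: "Proportion of participants with treatment-emergent AEs (TEAEs) is the primary safety endpoint of the study". Its next sentence is: "No statistical comparison will be provided for proportion of participants with TEAE". SAP 7.1.7 then sets out what is shown: "The number and percentage of participants who experienced at least 1 TEAE will be provided", by treatment group. It also plans "A brief, high-level summary of the number and percentage of participants who experienced at least 1 TEAE in the categories described above".

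The readable text of neither document plans a difference, a ratio or a confidence interval for the TEAE proportion.

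**The concern.** The trial is placebo-controlled, and Protocol 1.3 says that the blinded design will allow a stringent evaluation of safety as well as efficacy. Protocol 1.6 notes that some risks may not have been evident in studies of sicker patients. A placebo arm informs on harm through the contrast between arms, and the plan gives no measure of that contrast or of its precision.

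Other parts of the SAP do more. Baseline characteristics are tested between arms (SAP 5.1 and 5.2). The primary efficacy endpoint gets a hazard ratio with a 95% CI (SAP 6.1.3). Most secondary efficacy endpoints are compared without multiplicity adjustment (SAP 3.5 and 6.2.1).

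The early stop makes precision more important. SAP 2.1.1 records that enrollment stopped after 584 participants were randomized, of 1264 planned, and that the planned DMC analysis was not performed. Similar percentages in two arms of this size are compatible with a moderate excess on RDV, and the planned table would not say how large.

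**Working it through.** **Figures in the plan.** Neither document gives a rate, margin, power or precision for the TEAE endpoint, so there is no TEAE figure to reproduce. The stated sample size rests on efficacy alone, and it does reproduce:

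- HR = ln(1 − 0.066) / ln(1 − 0.12) = 0.534, as stated.
- Events = 1264 × 0.95 × 0.093 = 111.7.
- With R² = 0 and σ² = 0.25 in the Protocol 8.9 formula, power is 91.2%, in line with the stated figure of more than 90%.

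That calculation says nothing about TEAE precision.

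**Inputs for TEAE precision**

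- Planned size: 632 per arm (Protocol 8.9).
- Randomized: 584 (SAP 2.1.1). Assuming an even split and all dosed, 584 / 2 = 292 per arm.
- TEAE rate p, taken as equal in both arms: assumed, from 10% to 50%.

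**Formula.** The 95% half-width for a difference of two proportions (Wald approximation) is 1.96 × √(2p(1 − p)/n).

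| Assumed p | 2p(1 − p) | n = 292 per arm | n = 632 per arm |
|---|---|---|---|
| 10% | 0.18 | 1.96 × √(0.18/292) = 4.9 points | 3.3 points |
| 30% | 0.42 | 1.96 × √(0.42/292) = 7.4 points | 5.1 points |
| 50% | 0.50 | 1.96 × √(0.50/292) = 8.1 points | 5.5 points |

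The early stop widens the interval by √(632/292) = 1.47. If the observed rates were equal, an excess of up to about 5 to 8 points would not be excluded, depending on the rate.

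**Why an interval rather than a test.** With 292 per arm, a two-sided 0.05 test has 80% power only for an increase of about 8 to 12 points over baseline rates of 10% to 50%. With 632 per arm this is about 5 to 8 points. A non-significant p-value would therefore say little, whereas the interval shows directly what remains possible.

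**The case against.** The strongest reply is that the SAP does what the protocol asks. The protocol plans TEAEs descriptively, the safety objective has no hypothesis or margin, and the SAP states its choice openly. This stands.

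Three stronger readings are tempting, and the documents do not support them:

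- *The endpoint has no estimate.* It is worded as a proportion, and SAP 7.1.7 gives the number and percentage by treatment group. Those are its point estimates. The arms can also be compared side by side for Grade 3 or higher, drug-related, serious and discontinuation-related events, and for deaths. What is absent is a between-arm measure and its precision.
- *The SAP dropped a planned comparison.* The chi-square or Fisher rule for other proportions in Protocol 8.5.2 belongs to the efficacy section. Protocol 8.6 plans no comparison of TEAEs.
- *The plan treats equal percentages as proof of safety.* Nothing in either document says so.

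It can also be said that anyone could compute the interval from the published counts. That is true, but such an interval would not be prespecified or shown beside the percentages. Finally, the early stop explains only part of the imprecision: even with 632 per arm the half-width reaches 5.5 points at a 50% rate.

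**Conclusion.** The point holds as a reporting gap of minor weight. The primary safety endpoint will appear as n (%) per arm, and a reader will not see from the report what excess of TEAEs a placebo-controlled trial of this size can rule out. No inference is wrong and no type I error is affected.

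The half-width of 4.9 to 8.1 points rests on two assumptions that the documents do not settle: TEAE rates between 10% and 50%, and about 292 dosed participants per arm. Fewer dosed participants or an uneven split would widen it somewhat.

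**What to change.** Replace the second sentence of SAP 7.1.6 with:

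> The difference in the proportion of participants with any TEAE (RDV minus placebo) will be given with a 95% CI (Miettinen-Nurminen) for descriptive purposes; no hypothesis test will be done.

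The result fits in the high-level summary table already planned in SAP 7.1.7. It needs no new data and spends no alpha. Under SAP Section 1, the change can be made before the SAP is finalized, or documented in the CSR if made later.

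The same display for Grade 3 or higher and serious TEAEs is optional, since these are not primary endpoints. If serious TEAEs are shown, a footnote should say that they include COVID-19 hospitalizations and so partly reflect efficacy: in-patient hospitalization is a seriousness criterion (Protocol 7.1.2), and AEs are collected regardless of cause (Protocol 7.3.2).

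The downside is more prominence for imprecise safety differences, and some readers will treat an interval as a test. The label *descriptive* and the absence of a p-value limit that risk.

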#### **7.1.6.1.      Definition of Treatment-Emergent Adverse Events**

Treatment-emergent adverse events (TEAEs) are defined as 1 or both of the following:

- Any AEs with an onset date on or after the study drug start date and no later than 30 days after permanent discontinuation of study drug
- Any AEs leading to premature discontinuation of study drug.

#### **7.1.6.2.      Incomplete Dates**

If the onset date of the AE is incomplete and the AE stop date is not prior to the first dosing date of study drug, then the month and year (or year alone if month is not recorded) of onset determine whether an AE is treatment emergent. The event is considered treatment emergent if both of the following 2 criteria are met:

- The AE onset date is the same as or after the month and year (or year) of the first dosing date of study drug, and
- The AE onset date is the same as or before the month and year (or year) of the date corresponding to 30 days after the date of the last dose of study drug

An AE with completely missing onset and stop dates, or with the onset date missing and a stop date later than the first dosing date of study drug, or with the onset date missing and the AE is marked as ongoing, will be considered to be treatment emergent. In addition, an AE with the onset date missing and incomplete stop date with the same or later month and year (or year alone if month is not recorded) as the first dosing date of study drug will be considered treatment emergent.

### 7.1.7. Summaries of Adverse Events and Deaths

Treatment-emergent AEs will be summarized based on the Safety Analysis Set.

The number and percentage of participants who experienced at least 1 TEAE will be provided and summarized by SOC, High lever term (HLT), PT, and treatment group. For other AEs described below, summaries will be provided by system organ class, PT, and treatment group:

- Grade 3 or higher treatment-emergent AEs
- All treatment-emergent study drug-related AEs
- Grade 3 or higher treatment-emergent study drug-related AEs
- All treatment-emergent SAEs
- All treatment-emergent study drug-related SAEs
- All treatment-emergent AEs that caused premature discontinuation from study drug

TEAE and study drug related TEAE will summarized by system organ class, PT, Severity and treatment group.

A brief, high-level summary of the number and percentage of participants who experienced at least 1 TEAE in the categories described above, and treatment emergent deaths will be provided by treatment group. Treatment-emergent death refers to deaths that occurred between the first dose date and the last dose date plus 30 days (inclusive).

Multiple events will be counted only once per participant in each summary. Adverse events will be summarized and listed first in alphabetic order of SOC and HLT within each SOC (if applicable), and then by PT in descending order of total frequency within each SOC. For summaries by severity grade, the most severe grade will be used for those AEs that occurred more than once in an individual participant during the study.

In addition to the above summary tables, all treatment-emergent AEs, treatment-emergent AEs with Grade 3 or higher, treatment-emergent study drug-related AEs, and treatment-emergent study drug-related AEs with Grade 3 or higher, will be summarized by PT only, in descending order of total frequency.

In addition, data listings will be provided for the following:

- All AEs
- Study-Drug-Related AEs
- AEs with severity of Grade 3 or higher
- SAEs

- Study-Drug-Related SAEs
- Deaths
- AEs leading to premature discontinuation of study drug

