## 7. ADVERSE EVENTS AND TOXICITY MANAGEMENT

### 7.1. Definitions of Adverse Events and Serious Adverse Events

#### 7.1.1. Adverse Events

An AE is any untoward medical occurrence in a clinical study participant administered an investigational product, which does not necessarily have a causal relationship with the treatment. An AE can therefore be any unfavorable and/or unintended sign, symptom, or disease temporally associated with the use of an investigational product, whether or not the AE is considered related to the investigational product. AEs may also include pre- or post-treatment complications that occur as a result of protocol-specified procedures or special situations (Section 7.7).

An AE does not include the following:

- Medical or surgical procedures such as surgery, endoscopy, tooth extraction, and transfusion. The condition that led to the procedure may be an AE and must be reported.
- Preexisting diseases, conditions, or laboratory abnormalities present or detected before the screening visit that do not worsen
- Situations where an untoward medical occurrence has not occurred (eg, hospitalization for elective surgery, social and/or convenience admissions)
- Overdose without clinical sequelae (Section 7.7.1)
- Any medical condition or clinically significant laboratory abnormality with an onset date before the consent form is signed and not related to a protocol-associated procedure is not an AE. It is considered to be preexisting and should be documented as medical history.
- Preexisting events or conditions that increase in severity or change in nature after the consent form is signed or as a consequence of participation in the clinical study will be considered AEs.

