#### 7.1.2. Serious Adverse Events

A SAE is defined as an event that, at any dose, results in the following:

- Death
- Life-threatening (Note: The term “life-threatening” in the definition of “serious” refers to an event in which the participant was at risk of death at the time of the event; it does not refer to an event that hypothetically might have caused death if it were more severe.)
- In-patient hospitalization or prolongation of existing hospitalization
- Persistent or significant disability/incapacity

- A congenital anomaly/birth defect
- A medically important event or reaction: such events may not be immediately life-threatening or result in death or hospitalization but may jeopardize the participant or may require intervention to prevent one of the other outcomes constituting SAEs. Medical and scientific judgment must be exercised to determine whether such an event is a reportable under expedited reporting rules. Examples of medically important events include intensive treatment in an emergency room or at home for allergic bronchospasm; blood dyscrasias or convulsions that do not result in hospitalization; and development of drug dependency or drug abuse.

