### **8.9. Sample Size**

The total sample size of the study will be approximately 1264 participants.

The sample size computation is based on proportions of COVID-19 related hospitalization or all-cause death by Day 28 for the RDV and placebo treatment groups. The sample size needed for a 1:1 randomization using a 2-tailed test at level  $\alpha$  is given by:

$$\frac{(z_{1-\alpha/2} + z_{1-\beta})^2}{P(1 - R^2)\sigma^2 B^2}$$

Where P is the overall rate of COVID-19 related hospitalization or all-cause death, B is the log hazard ratio,  $\sigma$  is the standard deviation of treatment indicator variable, R is the R-Squared that is obtained when treatment indicator variable is regressed on the other covariates, and  $z_{1-\alpha/2}$  and  $z_{1-\beta}$  are the 1- $\alpha/2$  and 1- $\beta$  quantiles of the standard normal distribution.

A sample size of 1264 participants (632 in each group with 1:1 randomization) achieves > 90% power to detect a ratio of 0.55 (RDV to placebo in proportion of COVID-19 related hospitalization or all-cause death, which is equal to a hazard ratio of 0.534) using a 2-sided significance level of 0.05 assuming the overall hospitalization or death rate is 9.3% (12% in the placebo group and 6.6% in the RDV group) and a 5% drop out rate. The sample size provides approximately 80% power to detect smaller treatment effect size with a ratio of 0.60 (RDV to placebo), assuming a 2-sided significance level of 0.05 and the overall hospitalization or death rate is 9.6% (12% in the placebo group and 7.2% in the RDV group) and a 5% drop out rate.

The sample size calculation was done using software PASS (Version 14.0, module of Cox regression for survival).

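### The headline TEAE, Grade 3+ and SAE totals count COVID-19 progression, and SAP 7.1.7 plans no participant-level total without it

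*SAP*

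**What the plan says.** SAP 7.1.6 states: "Proportion of participants with treatment-emergent AEs (TEAEs) is the primary safety endpoint of the study". It adds: "No statistical comparison will be provided for proportion of participants with TEAE". The result will therefore be read descriptively.

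Protocol 7.1.1 defines an adverse event as "any untoward medical occurrence in a clinical study participant administered an investigational product, which does not necessarily have a causal relationship with the treatment". It also counts as adverse events "Preexisting events or conditions that increase in severity or change in nature after the consent form is signed". Its list of what is not an adverse event does not mention the disease under study. Protocol 7.1.2 makes death a seriousness criterion, and also "In-patient hospitalization or prolongation of existing hospitalization". Protocol 7.3.2 has all adverse events collected whatever their cause. SAP 7.1.6.1 runs the treatment-emergent window from the start of study drug to 30 days after it is permanently stopped.

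On all TEAEs, SAP 7.1.7 states: "The number and percentage of participants who experienced at least 1 TEAE will be provided and summarized by SOC", and then by high-level term and preferred term. Grade 3 or higher TEAEs and SAEs are tabulated by class and preferred term. Drug-related TEAEs, drug-related Grade 3+ TEAEs and drug-related SAEs have their own tables. A high-level summary gives the number of participants with at least one event in each category, and each participant counts once per summary. No category excludes COVID-19 events, and no grouped COVID-19 category is planned.

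**The concern.** The primary efficacy endpoint (SAP 6.1.1) is COVID-19 related hospitalization or all-cause death by Day 28. Under the definitions above, nearly all of its events are also TEAEs, and most are SAEs. If remdesivir works, its arm will show fewer participants with a TEAE, a Grade 3+ TEAE and an SAE because of efficacy alone. An excess of unrelated or drug-caused events on remdesivir would be offset in those totals. Safety is the second primary objective, and the totals are the figures most likely to be quoted for it. As planned, they mix the two effects, and a reader cannot take them apart at participant level.

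**Working it through.** **The plan's own figure.** Protocol 8.9 assumes "12% in the placebo group and 6.6% in the RDV group". The hazard ratio is ln(1 − 0.066)/ln(1 − 0.12) = 0.534, as stated. With 5% dropout, the expected events are 1264 × 0.95 × 0.093 = 111.7. The protocol's Cox formula with treatment variance 0.25 and R² = 0 (my assumption; no value is given) yields 91.2% power, in line with the stated figure of more than 90%. The documents state no figure for the safety point itself.

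**Window.** With the last dose on Day 3, the treatment-emergent window ends about Day 33 (3 + 30). With only one dose it ends about Day 31. Both cover Day 28.

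**Overlap in participants.** SAP 2.1.1 reports 584 randomized, taken here as 292 per arm. At planned rates, progression gives 0.12 × 292 = 35 participants on placebo and 0.066 × 292 = 19 on remdesivir.

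**Model.** Let h be the progression rate and b the rate of non-COVID SAEs, with P for placebo and R for remdesivir. Assume the two kinds of event are independent and that every endpoint event is an SAE. The documents give no value for b, so a range is shown.

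- Any-SAE total: 1 − (1 − h)(1 − b).
- Apparent advantage when b is the same in both arms: (1 − b)(h_P − h_R).
- Excess b_R − b_P at which the two totals are equal: (1 − b_P)(h_P − h_R)/(1 − h_R).

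**Equal non-COVID rates, planned progression.**

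- b = 1%: 12.9% vs 7.5% (placebo vs remdesivir).
- b = 2%: 13.8% vs 8.5%.
- b = 5%: 16.4% vs 11.3%.

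The gap is 0.99 × 0.054 = 5.3 points down to 0.95 × 0.054 = 5.1 points, all of it efficacy.

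**Excess cancelled in the total, in percentage points.** The SAE columns use b_P of 1%, 2% and 5%. The TEAE columns apply the same formula to any TEAE, with an assumed non-COVID background of 30%, 40% and 50%.

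| Progression, P vs R | (h_P − h_R)/(1 − h_R) | SAE 1% | SAE 2% | SAE 5% | TEAE 30% | TEAE 40% | TEAE 50% |
|---|---|---|---|---|---|---|---|
| 12% vs 6.6% (plan) | 0.054/0.934 = 0.0578 | 5.7 | 5.7 | 5.5 | 4.0 | 3.5 | 2.9 |
| 6% vs 3.3% (half) | 0.027/0.967 = 0.0279 | 2.8 | 2.7 | 2.7 | 2.0 | 1.7 | 1.4 |
| 3% vs 1.65% (quarter) | 0.0135/0.9835 = 0.0137 | 1.4 | 1.3 | 1.3 | 1.0 | 0.8 | 0.7 |

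The lower rows matter because SAP 2.3 gives lower hospitalization rates as a reason for stopping enrollment.

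**What a separate count would show.** Take planned progression with non-COVID SAE rates of 2% and 7.7%. Both any-SAE totals are 13.8%. A count without COVID-19 events would show about 6 versus 22 participants (0.02 × 292 and 0.0767 × 292). As a yardstick only, since no test is planned, a comparison of 2% with 7.7% at 292 per arm would have 89% power.

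**The case against.** The case for leaving the plan alone has weight.

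- **Planned detail.** COVID-19 preferred terms have their own rows in the TEAE and SAE tables. A harm concentrated in one or a few unrelated terms would be visible there.
- **Causality.** Protocol 7.2.1 says ineffective treatment is not to be judged causally related, so the drug-related tables should largely leave progression out. Blinding should make attribution errors similar in both arms.
- **Other safety data.** Graded laboratory abnormalities and vital signs are summarized separately, and no test on TEAEs can yield a false formal conclusion.
- **Size.** The 12% is an efficacy planning rate, not an SAE rate. SAP 1.3 bases it on a figure for hospitalizations or emergency department visits. The endpoint requires at least 24 hours of acute care, whereas the seriousness criterion is in-patient admission. SAP 6.4 mentions very few participants progressing to oxygen, a different endpoint that points the same way as SAP 2.3.
- **Unseen source.** The eCRF completion guidelines are not among the documents and may hold a rule for recording progression.

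These points limit the concern but do not remove it. Progression can be coded under several terms, such as pneumonia, hypoxia or dyspnoea, and SAP 7.1.7 plans no grouping. Protocol 5.3.2 lists hypoxia, fever and dyspnea among infusion-reaction signs, so those rows can mix disease and drug. A participant can appear in several rows, so rows cannot be added up to a participant count. The drug-related tables depend on case-by-case judgement where the signs overlap, and SAP 7.1.3 counts a missing relationship as related. If the completion guidelines do contain a rule, the SAP should cite it.

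**Conclusion.** The primary safety endpoint and the Grade 3+ and SAE totals mix efficacy with safety, and no planned participant-level total excludes COVID-19 progression. This is a cheap improvement. The planned tables remain valid.

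Under the stated assumptions, the any-SAE total could cancel a non-COVID excess on remdesivir of about 5.5 to 5.7 points at planned progression rates, 2.7 to 2.8 at half and 1.3 to 1.4 at a quarter. For any TEAE the figure is about 2.9 to 4.0 points at planned rates, because background events dominate. Progression short of admission also counts as an adverse event, but the documents give no rate for it and it is not in these figures.

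A reader might infer that no table separates progression at all, or that the safety objective is answered only by efficacy data. The documents do not support either reading. Preferred-term rows, drug-related tables and the laboratory and vital-sign summaries give partial separation. Harm is masked in the totals, not necessarily at preferred-term level.

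**What to change.** In SAP 7.1.7, keep every all-event table as planned. Beside them, add participant-level counts and percentages by arm for any TEAE, any Grade 3 or higher TEAE and any SAE, excluding a preferred-term list for COVID-19 and its direct manifestations. Put the list in SAP Appendix 2 and fix it before unblinding. The SAP already works this way elsewhere: Appendix 2 (item 20) uses prespecified term lists reviewed by medical monitors for baseline risk factors, and section 3.1 settles the analysis sets before the blind is broken.

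Do not extend the exclusion to every adverse event that occurs during a COVID-19 related admission. That could remove drug-caused events, and it would rest on the site's classification of the admission.

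The cost is three extra summaries and a blinded medical review of the list. The downside is that the list needs judgement, because some terms fit both the disease and a drug reaction. Showing both sets of counts side by side keeps that choice visible.
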